12.8 Vitiello Aggression Scale

Predatory-Affective Aggression Scale

Patien	t			
Rater_		Date		 
Check month	if any these behaviors is usual for this patient (i.e., it has o):	occurred a	t least	3 times during the last
		Y	YES	NO
1.	Non profitable damaging of own property	1	1	0
2.	Hides aggressive acts	1	1	0
3.	Exposes self to physical harm when aggressive	1	1	0
4.	Is aggressive without a purpose	1	1	0
5.	Can control own behavior when aggressive	1	1	0
6.	Aggression is unplanned, out of the blue	1	1	0
7.	Very careful to protect self when aggressive	1	1	0
8.	Completely out of control when aggressive	1	1	0
9.	Plans aggressive acts	1	1	0
10.	Steals	1	1	0

Scoring:

Predatory score: sum of items 2, 5, 7, 9, and 10 Affective score: sum of items 1, 3, 4, 6, and 8

Total score: difference of Predatory score minus Affective score/

Possible range of total score: from 5 (completely predatory) to -5 (completely affective)

Reference:

B. Vitiello et al. (1990), J. Neuropsychiatry Clin. Neurosciences 2:189-192.

12.9 Edinburgh Handedness Inventory

Subject Number:	 ate:

EDINBURGH HANDEDNESS INVENTORY

Please indicate your preferences in the use of hands in the following activities by putting + in the appropriate column. Where the preference is so strong that you would never try to use the other hand unless absolutely forced to, put + +. If in any case you are really indifferent, put + in both columns.

Some of the activities require both hands. In these cases the part of the task, or object, for which hand preference is wanted is indicated in brackets.

Please try to answer all the questions, and only leave a blank if you have no experience at all of the object or task.

		LEFT	RIGHT	
1	Writing			
2	Drawing			
3	Throwing			
4	Scissors			
5	Toothbrush			
6	Knife (without fork)			
7	Spoon			
8	Broom (upper hand)			
9	Striking Match (match)			
10	Opening box (lid)			
i	Which foot do you prefer to kick with?			
ii	Which eye do you use when using only one?			

# of LEFT	# of RIGHT	# RIGHT-#LEFT	# RIGHT + #LEFT
10 111 11 11 11 11 11 11 11 11 11 11 11	* 100		
(# RIGHT+ #LEFT)			

Oldfield, R.C. "The Assessment and Analysis of Handedness: The Edinburgh Inventory." Neuropsychologia, 9(1):97-113. 1971

12.10 PSAP Questionnaire

Subject ID:			Date	Imaging Procedu	ures Performed:	
		810P204 I	lmaging Center	Visit		
Section I:						
	SAP fMRI sesses points were sit on treatment on the side the second contract of the second contract on the second contract of the second	sions completo e earned by the ent only: ubject report to	ed? e subject?	medication d	N N lose?	_
Section II:						
Administer below ques	tionnaire to	the subject at	the end of the vi	sit		
"Thank you for participe like to hear from you to you could please answe	understand i	f there is some				
1. How easy was the g rate the game?	ame? On a s	cale from 1 to	5, where 1 is very	/ difficult and	5 is very easy, hov	v would you
	\circ	0	\circ	0	\circ	
	1	2	3	4	5	
2. What was the n	nost difficult	part of the gan	ne?			
3. What don't you	like about th	ne game? Choc	ose up to 3.			
◯ It takes u	p too much t	ime	◯ lt's	frustrating		
I didn't ea	rn too much		O It's	boring		
O It's pointle	ess					
4. Choose one to o	describe the	other player:				
○ Unbeatab	ole player		O Ba	ad player		
Good play	/er		0 0	ther		
Administered By (Initials	s/Date):					
Version 1.0						

12.11 MR Safety Questionnaire

Name:	Acct#:	Date:

SAND LAKE IMAGING

MAGNETIC RESONANCE (MR) PROCEDURE SCREENING FORM

Please read and CIRCLE YES OR NO if you have any of the following:

ABSC	ABSOLUTE CONTRAINDICATIONS		
YES	NO	Aneurysm clip (s)	
YES	NO	Pacemaker	
YES	NO	Implanted cardioverter defibrillator (ICD)	
YES	NO	Electronic implant or device	
YES	NO	Magnetically – activated implant or device	
YES	NO	Neuro-stimulation System	
YES	NO	Spinal Cord Stimulator	
YES	NO	Internal electrodes or wires	
YES	NO	Bone growth/ Bone fusion stimulator	
YES	NO	Cochlear, otologic, or other ear implant	
YES	NO	Tissue expander (ex: breast)	
Other			

POSS	POSSIBLE CONTRAINDICATIONS		
YES	NO	Any type of prosthesis (eye, penile, etc.)	
YES	NO	Heart valve prosthesis	
YES	NO	Eyelid spring or wire	
YES	NO	Any metallic fragment or foreign body	
YES	NO	Metallic Stent, filter, or coil	
YES	NO	Insulin or other infusion pump	
YES	NO	Shunt (spinal or intraventricular)	
YES	NO	Medication patch (nicotine, nitroglycerine)	
YES	NO	Implanted drug infusion device	
Other			

NEED	NEED TO KNOW FOR POSSIBLE ARTIFACT		
YES	NO	Wire Mesh Implant	
YES	NO	Dentures	
YES	NO	Surgical staples, clips, metallic sutures	
YES	NO	Joint Replacement (hip, knee, etc)	
YES	NO	Bone/joint pin, screw, nail, wire, plate, etc	
YES	NO	IUD, diaphragm, or pessary	
YES	NO	Tattoo or permanent makeup	
YES	NO	Body Piercing	
YES	NO	Hearing Aid (removed before entering MR	
		room)	
Other			

Surgical Hx: Pregnancy Status: LMP:

CAUTION

Before entering the MR environment or MR system room, you must remove all metallic objects including: weapons including pistols, hearing aids, dentures, partial plates, keys, beeper, cell phone, eyeglasses, hair pins, barrettes, jewelry, body piercing jewelry, watch, safety pins, paperclips, money clips, credit cards, bank cards, magnetic strip cards, coins, pens, pocket knife, nail clipper, tools, clothing with metal fasteners, clothing with metallic threads.

Please consult the MRI Technologist or Radiologist if you have any question or concerns BEFORE entering the MRI system room.

NOTE: You may be advised or required to wear ear plugs or other hearing protection during the MR system room.

I have read the above statement and acknowledge it is my responsibility to remove the listed items before entering the MRI room in order to prevent damage to Sand Lake Imaging equipment and my personal items. Sand Lake Imaging is no responsible for damage to personal items not removed before entering MRI room

Patient or Guardian Signature:	
Date:	
HEIGHT:	
WEIGHT:

1 INTRODUCTION

The purpose of this statistical analysis plan (SAP) is to ensure the credibility of the study findings by specifying the statistical approaches to the analysis of the data. This SAP covers the planned analyses of all data collected on the eCRFs, and will identify handling of data issues. The statistical analysis plan presented in this document will supersede the statistical analysis methods described in the clinical protocol. Any deviations/changes from the planned analyses described in this SAP will be identified, with justification, in the appropriate section of the clinical study report. This SAP is based on the clinical study protocol 810P204, version 3.0, dated 12 Apr 2019 and its associated electronic case report forms (eCRF).

2 **STUDY OBJECTIVES**

The primary objective is to evaluate the effect of SPN-810 treatment on brain activity in subjects aged 8-12 years with ADHD and IA using functional Magnetic Resonance Imaging (fMRI).

Secondary objectives are to evaluate the effect of SPN-810 treatment on:

- The functional connectivity between brain regions using resting-state fMRI (rs-fMRI)
- The concentration of neurotransmitters glutamate and gamma-aminobutyric acid (GABA) using Magnetic Resonance Spectroscopy (MRS)
- Safety of SPN-810

Tertiary objectives are to evaluate the following:

- Pharmacokinetics (PK) of Molindone
- Effect of SPN-810 treatment on the Clinical Global Impression-Severity (CGI-S) and -Improvement (CGI-I) scores
- Effect of SPN-810 on the Retrospective-Modified Overt Aggression Scale (R-MOAS) score.

3 **ENDPOINTS**

Primary Endpoint is the change in the whole brain in BOLD fMRI contrast in response to the PSAP task from Baseline (Visit 2) to Visit 5.

Secondary Endpoints are:

- Change in functional connectivity as reflected in the Fisher's Z-transformation of correlation coefficients between brain regions during rs-fMRI from Baseline (Visit 2) to Visit 5.
- Change in the concentrations of neurotransmitters GABA and glutamate in the anterior cingulate cortex (ACC) from Baseline (Visit 2) to Visit 5 as determined by MR spectroscopy.
- Safety endpoints:
 - 1) Adverse events.
 - 2) Safety scales (Simpson-Angus Scale, Barnes Akathisia Rating Scale [BARS], and Abnormal Involuntary Movement Scale [AIMS]).
 - 3) Clinical laboratory tests (hematology, chemistry, and urinalysis).

- 4) Vital signs.
- 5) Electrocardiograms (ECGs).
- 6) Columbia-Suicide Severity Rating Scale (C-SSRS).

4 STUDY DESIGN

This is a multi-center, double-blind, randomized (1:1), placebo-controlled, parallel-group, 2-arm study.

The study will screen approximately 40 male and female subjects, aged 8-12 years inclusive, with ADHD and IA, to achieve an approximate enrollment of 30 subjects.

This study consists of 3 phases: Pre-Treatment, Treatment, and Conversion/Taper.

The Pre-Treatment Phase comprises of Screening and a Baseline MRI Visit for a total duration of up to 30 days. Following Screening (Visit 1), eligible subjects will proceed to the Baseline MRI visit (Visit 2) at the Imaging Center, where the brain MRI scans will be performed. At Visit 3, eligible subjects will be randomized to study medication or placebo.

Eligible subjects will follow a dose-titration schedule with initial dosing at approximately every 2 days until the target dose (36 mg/day) is reached. The final dose will be maintained for 2 weeks (Maintenance period) during which time subjects will return for PK sampling (Visit 4) prior to receiving the final MRI scan at the Imaging Center (Visit 5). At the intervening visit during the maintenance phase (Visit 4), subjects will be given the option to taper down/discontinue study medication or convert to an ongoing OLE study (810P304) upon completion of the current study and will receive the blinded taper or the conversion study medication kit. Subjects will return to the study site for a final EOS visit (Visit 6), after completing the 1-week Taper or Conversion phases. Subjects who choose to convert into the ongoing OLE (SPN-810 304) will enter the study at a dose of 18 mg/day SPN-810.

This study is designed to use fMRI in conjunction with the PSAP aggression task. MR imaging parameters for the PSAP Task were optimized in the non-interventional 810P204a study that was conducted by the Sponsor in typically developing children 8-12 years of age.

5 **ANALYSIS VARIABLES**

5.1 **Primary Variables**

The primary analysis variable will be the treatment effect of SPN-810 on the change in BOLD fMRI contrast associated with the aggressive response from Baseline (Visit 2) to Visit 5 measured in subjects with ADHD and IA participating in the PSAP aggression Task.

Briefly, the primary endpoint is the change in brain activity measured by a change in BOLD response in brain regions during provocation or during the aggressive response relative to the monetary response at baseline and following 4 weeks treatment with SPN-810, compared to placebo.

Behavioral data may allow calculation of the aggressive score, defined as the number of Option 2 presses (aggressive response) divided by the total number of button presses and the number of provocations received.

5.2 **Secondary Variables**

5.2.1 Functional Connectivity

Resting-state data will be used to generate maps of functional connectivity within brain networks and/or ROI and will be stored in a correlation matrix. To investigate brain networks, a seed to whole brain correlation map may be used to investigate changes in network connectivity. All correlation coefficients will be converted to a z-score using Fisher's Z-transformation to normalize values.

To look at connectivity between ROIs, seed to seed correlation values will be calculated. All correlation coefficients will be converted to a z-score using Fisher's Z-transformation to normalize values. In addition, the relevant variables for the correlation matrices will be calculated by Northwestern University.

5.2.2 GABA and Glutamate Brain Concentrations

The concentrations of neurotransmitters Glu and GABA will be achieved during the MRS scan and evaluated in the anterior cingulate cortex (ACC).

5.3 Safety Variables

Safety assessments will focused on adverse event (AE) occurrences (including its severity, relationship to study drug, SAE (Yes/No), and, action taken, and outcome), laboratory tests (e.g. Hematology, Chemistry, Urinalysis, urine drug test, and urine pregnancy test), vital signs, height/weight measurements, medical history, physical examinations, ECGs and special safety tests including Simpson-Angus Scale (SAS), Barnes Akathisia Rating Scale (BARS), Abnormal Involuntary Movement Scale (AIMS), and Columbia-Suicide Severity Rating Scale (C-SSRS).

5.4 Tertiary Variables

The tertiary variables include the following:

- 1) The pharmacokinetic variables of interest will include (1) Apparent clearance (CL/F); (2) Apparent volume of distribution (V/F) of Molindone in the study population.
- 2) Clinical Global Impression scales [Severity of illness (CGI-S) and global improvement (CGI-I)] will be evaluated. Both scales will be rated on a scale of 1 to 7 with 7 being "extremely ill" (CGI-S) or "very much worse" (CGI-I) respectively. They will be administered at Visit 1 (CGI-S only), Visit 4 and 6.
- 3) Retrospective-Modified Overt Aggression Scale (R-MOAS) was developed to gauge the severity of aggressive behavior (Blader et al., 2009). Parents rate the frequency over the past week of 16 aggressive behaviors in 4 areas: verbal aggression; physical aggression toward others; aggression toward oneself; and destruction or hostile misuse of property. Numeric weighting amplifies the seriousness of more harmful behaviors in the total score. The R-MOAS will be administered at Visit 1, Visit 4, and Visit 6.

5.5 Other Special Tests

Other special tests will be administered in the clinic as per Schedule of Events in the protocol. They are MINI-KID, Vitiello Aggression Scale, and Edinburgh Handedness Inventory.

6 STATISTICAL METHODS

6.1 General Notions

The primary and secondary endpoint data (Section 7.4 and 7.5) were handled and analyzed by [name]., Department of Radiology, Northwestern University, Chicago, IL 60611. All other data were analyzed at Supernus using SAS version 9.

Tabular summaries of the data collected during the study will provide a general description of the subjects studied and an overview on brain functioning, GABA and Glu levels, and safety results by study treatment group. Due to early termination of the study, all statistical analyses will be descriptive without any hypothesis testing. Continuous variables will be summarized using descriptive statistics [number of subjects, mean, standard deviation (SD), median, and minimum and maximum]. Categorical (nominal) variables will be summarized by reporting the frequency and percentage of subjects in each category.

In addition, subject data listings, as specified in Sections 16.2 and 16.4 of ICH Guidance E3, will be provided. Analysis processing will be performed before the database is released. Any deviation from the statistical plan will be documented and described in the final report.

6.2 Handling of Dropout or Missing Data

No imputation will be implemented.

7 **STATISTICAL ANALYSIS**

7.1 Analysis Populations

The population of "all enrolled subjects" consists of all those screened subjects who meet the requirements for study participation and have completed the imaging procedures prior to randomization. The following populations will be analyzed:

Randomized Population: The population of "all randomized subjects" consists of all those enrolled subjects who complete the Baseline Period including imaging scans, meet the inclusion/exclusion criteria and are randomized.

Safety Population: includes all subjects randomized and who received at least 1 dose of study drug.

Completed Population: includes all subjects randomized, who have baseline imaging scans (including the anatomical scan) and post-treatment imaging scans.

PK population: includes all subjects in the safety population who had at least 1 PK sample drawn which had a quantifiable concentration of Molindone.

7.2 Disposition, Demographic and Baseline Characteristics, Protocol Deviations

Subject disposition, reason for discontinuation from the study (randomized population), demographic characteristics (completed population), major protocol deviations during the study (completed population), medical history (safety population), and concomitant medications (safety population) will be reported in the summary tables. The prior and concomitant medications will be coded using WHO

Drug Dictionary (WHODD, March 1 2019 B3 format) for PT and Anatomical Therapeutic Chemistry classification.

7.3 **Study Medication Exposure and Compliance**

Duration of treatment exposure is defined as the total number of days a subject is exposed to study treatment. This will be calculated for each subject by taking the difference between the date of last dose *minus* the date of the first dose *plus* 1 (date of last dose – date of first dose +1). Duration of treatment exposure will be summarized using descriptive statistics.

Percent of study medication (SM) compliance will be calculated as:

$$SM\ Compliance\ (\%) = 100*(D-R)/[4*(D_L-D_F+1)]$$

Where D=number of tablets dispensed, R=number of tablets returned,

D_L=date of last dose, and D_F=date of first dose

The SM compliance will be summarized as both categorical variable (<80%, 80-120%, and >120%) and a continuous variable using descriptive statistics.

Summaries of treatment exposure and compliance will be presented separately for the Titration period only, Maintenance period only, and Titration and Maintenance Combined.

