4.2.7 Pharmacokinetic Blood Sampling

5 TREATMENTS

5.1 Treatments Administered

SPN-810

Subjects will take molindone hydrochloride extended-release tablet (SPN-810) or placebo twice each day (BID) with or without food, in the morning and in the evening, in addition to their stable dose of the optimized ADHD medication. Subjects should start the first dose the morning following Visit 3. Subjects will be randomized to one of the 2 treatments at the completion of Visit 3. Subjects will be titrated to the final randomized total daily dose (TDD).

Reference Treatment

Treatment 1: Placebo (PBO) tablets (2 tablets), BID

Test Treatment

Treatment 2: SPN-810, 36 mg (2 tablets) TDD, BID

ADHD Medication

The Investigator is not allowed to adjust the FDA-approved ADHD monotherapy medication and/or its dose at any time during the course of this study.

5.1.1 *Identity of Investigational Product(s)*

Study medication and reference (matching placebo) products are either purple (3 mg) or yellow (9 mg) round tablets which are printed with the appropriate dose strength in a black underscored font ("3" or "9").

A sufficient quantity of medication will be dispensed for the subject to take the designated dose every day until the next visit to the office, according to Table 1.

Each study medication blister card will contain combinations of SPN-810 and/or placebo tablets, which will supply a subject with 7 days of dosing with one additional dosing for lost product and/or to account for visit delays associated with patient schedules.

A single study medication kit contains a total of 6 pre-packaged blister cards (2 Titration blister cards, 2 Maintenance blister cards, 1 Taper blister card and 1 Conversion blister card) and is marked with a unique 4-digit study medication kit number.

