5.1.3 Method of Assigning Subjects to Treatment Groups

Allocation of the study medication will be completed centrally through the use of an interactive web response system (IWRS) that will determine which kit to assign to the subject. The final randomization schedules will be created by a designated unmasked statistician using SAS (SAS Institute, Cary, North Carolina, Version 9.2 or higher). Separate schedules for subject randomization and drug kit list will be created. The randomization scheme assigns treatment codes to each randomization number in a 1:1 ratio.

Upon enrollment to the study, subjects will be assigned site (01-99) and subject numbers in the sequence that they are entered. Subjects who minimally complete the two (2) PSAP sessions and the MPRAGE structural scan and meet all eligibility criteria will be assigned kit numbers, according to the randomization schedule, by using the IWRS.

5.1.4 *Treatment Replacement*

In the event that a subject's original kit is lost, damaged, or consumed prior to the end of treatment, the Investigator will consult the IWRS, which will specify a replacement kit number to be sent to the site. Separate reserve supplies will not be provided to the Investigators.

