7.6 Protocol Deviations

Protocol deviations will be presented in listings. If applicable, the number and percent of subjects within each type of protocol deviation will be presented using discrete summary statistics. Protocol deviations may include, but are not limited to:

- Non-compliance with any scheduled study visit
- Compliance with study treatment <80%
- Disallowed concomitant medications
- Non-compliance with study inclusion or exclusion criteria
- Non-compliance with study assessment procedures

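### SAP 7.3 counts lost, unreturned tablets as taken, so compliance can mask low intake or put a fully adherent child above 120%

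*SAP*

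**What the plan says.** SAP 7.3 defines percent compliance as 100 × (D − R) / [4 × (D_L − D_F + 1)]. The numerator terms are given as "Where D=number of tablets dispensed, R=number of tablets returned" and the dates as "D_L=date of last dose, and D_F=date of first dose". Protocol 7.7 uses the same numerator. The result is sorted into below 80%, 80–120% and above 120%, and is "presented separately for the Titration period only, Maintenance period only, and Titration and Maintenance Combined". SAP 6.2 rules out imputation.

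The supply rules are in the protocol:

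- Section 5.1.1: each blister card holds tablets "which will supply a subject with 7 days of dosing with one additional dosing for lost product", and the spare also covers visit delays. A kit has two Titration, two Maintenance, one Taper and one Conversion card.
- Section 5.1.4: "In the event that a subject's original kit is lost, damaged, or consumed prior to the end of treatment", the IWRS names a replacement kit.
- Section 5.1.2: subjects are to bring back all supplies, used or not, with the empty packaging.
- Section 7.6: "Compliance with study treatment <80" per cent is listed as a possible protocol deviation.

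Neither document says how a documented loss, or a card that never comes back, enters D or R.

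**The concern.** The formula allows a dispensed tablet two fates: returned or taken. The protocol plainly expects a third, lost, since it packs for it and replaces for it. Lost tablets raise the score, and replacement tablets enter D as well.

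The error can mislead in both directions. A child with poor intake who does not bring cards back can be classed as compliant, and the below-80% flag is missed. A fully adherent child whose supply was lost and replaced can land in the row that should signal over-use. Section 5.1.4 also replaces kits consumed early, so that row cannot separate a child who lost tablets from one who took too many. Because SAP 7.7.1 drops the PK analysis, the tablet count is the remaining planned measure of how much drug was taken. The exposure summary counts only days.

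**Working it through.** **Inputs**

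- Four tablets a day: protocol 5.1 gives "Treatment 1: Placebo (PBO) tablets (2 tablets), BID", which agrees with the 4 in the formula. I assume it holds during titration too; the active-arm cells of protocol Table 2 are blank in the public copy.
- Tablets per card: 7 × 4 = 28 plus the spare. Reading one additional dosing as a single intake (2 tablets) gives 30; reading it as a day (4 tablets) gives 32. Both are assumptions, and both are carried through.
- Need: 4 × 28 = 112 tablets for the combined period (four cards), 4 × 14 = 56 for one period (two cards).
- Dosing dates span the whole period unless stated otherwise.

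The plan states no compliance figure to reproduce. As a check, an adherent child who returns all spares scores (120 − 8)/112 or (128 − 16)/112, which is 100% either way.

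**General form for an adherent child.** Let U be the unused tablets that were never returned. Then D − R = need + U and the score is 100 × (1 + U/need). It passes 120% only if U exceeds 0.2 × 112 = 22.4 tablets (combined) or 0.2 × 56 = 11.2 (one period). If all unused replacement product is returned, it cancels out of D − R, so it makes no difference whether the replacement comes as a card or as a kit.

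**Case 1: no cards returned, R entered as 0.** 120/112 = 107.1% or 128/112 = 114.3%, whatever the true intake. With 29 or 27 dosing days the range is 120/116 = 103.4% to 128/108 = 118.5%. If the last dose is on day 20, the score is 120/80 = 150% or 128/80 = 160%, which no longer reads as compliant.

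**Case 2: 60% true intake, one of two Maintenance cards not returned and entered as nothing returned.** The returned card shows 0.6 × 28 = 16.8 tablets used. The score is (16.8 + 30)/56 = 83.6% or (16.8 + 32)/56 = 87.1%, so the child is not flagged.

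**Case 3: adherent, one card lost after k days of use and replaced, all other leftovers returned.** U = card size − 4k.

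| k | Combined, 30 | Combined, 32 | One period, 30 | One period, 32 |
|---|---|---|---|---|
| 0 | 126.8% | 128.6% | 153.6% | 157.1% |
| 1 | 123.2% | 125.0% | 146.4% | 150.0% |
| 2 | 119.6% | 121.4% | 139.3% | 142.9% |
| 3 | 116.1% | 117.9% | 132.1% | 135.7% |
| 4 | 112.5% | 114.3% | 125.0% | 128.6% |
| 5 | 108.9% | 110.7% | 117.9% | 121.4% |
| 6 | 105.4% | 107.1% | 110.7% | 114.3% |

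**Case 4: adherent, all four treatment cards lost after k days and the kit replaced.** The score is (112 + 4 × card − 4k)/112. At day 21 it is 148/112 = 132.1% or 156/112 = 139.3%. The last day above 120% is day 24 with 30-tablet cards (136/112 = 121.4%) and day 26 with 32-tablet cards (136/112 = 121.4%). Beyond day 21 this supposes that no cards had gone back at Visit 4, where drug return is scheduled.

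**Case 5: adherent, an unused 30-tablet card damaged, returned and replaced.** D = 150, R = 30 + 8 = 38, and 112/112 = 100%.

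**The case against.** Dispensed minus returned is an ordinary pill count, its limits are well known, and the SAP carries it over from the protocol. Four more specific objections have force.

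1. A reader might infer that any replaced card takes an adherent child above 120%. It does not. The product must be lost, unreturned and lost early enough (Case 3), and a damaged card that comes back scores 100% (Case 5).
2. A reader might infer that the SAP prescribes 107–114% for cards not returned. It does not say that R is then 0. With imputation ruled out, one can equally argue that R, and so compliance, is missing. This stands, so Cases 1 and 2 are conditional on entering R as 0. What remains is that the SAP does not settle which reading applies.
3. A reader might worry that Taper or Conversion cards, dispensed at Visit 4, inflate D. The period summaries in SAP 7.3 already imply that these cards are out, so a stated limit only makes this explicit.
4. Protocol 5.1.4 replaces kits, and no card-level rule is given. This is correct, but Case 3 needs only that unused replacement product is returned, and Case 4 follows the kit rule directly.

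On impact, the objection is sound. SAP 6.1 makes all analyses descriptive after early termination, compliance defines no analysis population in SAP 7.1, and the below-80% item is only one deviation that may be listed.

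**Conclusion.** The point holds, at minor severity. SAP 7.3 treats lost, unreturned tablets as taken, although the protocol foresees such tablets, so the stated rule gives a wrong figure for the children concerned. Given four tablets a day in both periods, 30 or 32 tablets per card and full-period dosing dates:

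- With no cards returned and R entered as 0, the score is 107–114% whatever the intake.
- A fully adherent child can pass 120%: 127–129% combined for one whole unused card lost and replaced, and above 120% for loss of all four treatment cards up to about day 24–26.
- Loss after about two to three days of use of a single card can leave the combined score below 120%.

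The documents do not support a claim that the imaging endpoints, the analysis populations or a treatment comparison are affected. The consequence is confined to the descriptive compliance table and the below-80% flag.

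**What to change.** In SAP 7.3:

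1. Define tablets taken as D − R − L, where L is the number of tablets documented as lost or destroyed and not returned. Tablets already counted in R, such as damaged ones that came back or returned ones later destroyed at the site, must stay out of L.
2. State that D, R and L cover only the cards of the period being summarised.
3. Where a card is not returned and has no documented count, report that period as not evaluable in its own row, and do not set R to 0.

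The adherent child with one whole card lost and replaced then scores (150 − 8 − 30)/112 = 100%, or (160 − 16 − 32)/112 = 100%. The restriction on L matters: if the damaged, returned card of Case 5 were also put in L, those tablets would be subtracted twice, giving (150 − 38 − 30)/112 = 82/112 = 73%, a false flag.

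The cost is a change of SAP wording and a programming step. Some children will move to not evaluable. Protocol 5.1.2 names no field for lost tablets, so L has to be drawn from the accountability and IWRS reconciliation records. Where those are silent, not evaluable is the right class.
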